## 2.2 Safety Objectives

The co-primary safety objectives are to:

- Estimate the cumulative rate of secondary surgical interventions (SSIs) related to the optical properties of the IOL for the first operative eye up to Month 12 (Visit 5)
- Evaluate the mean monocular contrast sensitivity for the first operative eye, with and without glare for mesopic conditions and photopic conditions, at Month 12 (Visit 5)

The secondary safety objectives are to evaluate:

- Rates of cumulative and persistent adverse events (AEs) in first operative eyes at Month 12 (Visit 5) in comparison to the International Organization for Standardization (ISO) Safety and Performance Endpoint (SPE) rates as described in ISO 11979-7
- Visual disturbances using the Quality of Vision (QoV) questionnaire and QoV Supplemental Questions at Month 12 (Visit 5)

2.3

## 2.4 Clinical Parameters

- Projected Visual Acuity
- Target Refraction
- Axial Length
- Anterior Chamber Depth
- Keratometry
- Corneal Topography
- Manifest Refraction
- Patient-Reported Outcome Questionnaires

- Visual disturbances via the QoV and QoV Supplemental Questionnaire
- Spectacle independence via the PRSIQ
- Pupil Size (photopic and mesopic)
- Intraocular Pressure (IOP)
- Slit Lamp Examination
- IOL Tilt and Centration
- [REDACTED]
- Dilated Fundus Examination
- Posterior Capsule Assessment
- IOL observations
- Adverse Events
- Visual Acuity
- Contrast Sensitivity
- Defocus Curves

### **3. Study Variables**

#### **3.1 Primary Variables**

##### **3.1.1 PRIMARY EFFECTIVENESS VARIABLES**

The co-primary effectiveness variables are the following:

- Photopic monocular logarithm of the minimum angle of resolution (logMAR) BCDVA in first operative eyes at Month 6 (Visit 4)
- Photopic monocular logMAR near (40 cm) visual acuity with distance correction (DCNVA) in first operative eyes at Month 6 (Visit 4)

##### **3.1.2 PRIMARY SAFETY VARIABLES**

The co-primary safety variables are the following:

- Cumulative rate of SSIs related to the optical properties of the IOL in first operative eyes through Month 12 (Visit 5)
- Mean monocular distance contrast sensitivity (mesopic with and without glare at 1.5, 3, 6, and 12 cycles per degree (cpd) measured at 2.5 m, and photopic with and without glare at 3, 6, 12, and 18 cpd, measured at 2.5 m) in first operative eyes at Month 12 (Visit 5)

#### **3.2 Secondary Variables**

##### **3.2.1 SECONDARY EFFECTIVENESS VARIABLES**

The secondary effectiveness variables include the following:

- Photopic monocular logMAR intermediate (66 cm) visual acuity with distance correction (DCIVA) in first operative eyes at Month 6 (Visit 4)

### 3.2.2 SECONDARY SAFETY VARIABLES

The secondary safety variables include the following:

- Rates of cumulative and persistent AEs in first operative eyes through Month 12 (Visit 5), compared to the ISO SPE rates as described in ISO 11979-7
- Visual disturbances using the Quality of Vision (QoV) questionnaire and QoV Supplemental Questions at Month 12 (Visit 5)

### 3.3 Additional Effectiveness Variables

The additional effectiveness variables include the following:

- Photopic monocular logMAR BCDVA, [REDACTED], DCIVA (66 cm), and DCNVA in first operative eyes at Month 6 (Visit 4) and Month 12 (Visit 5)
- Mesopic monocular logMAR [REDACTED], DCIVA (66 cm), and DCNVA in first operative eyes at Month 6 (Visit 4) and Month 12 (Visit 5)
- Photopic binocular logMAR BCDVA, [REDACTED] DCIVA (66 cm), and DCNVA at Month 6 (Visit 4) and Month 12 (Visit 5)
- Mesopic binocular logMAR [REDACTED] DCIVA (66 cm), and DCNVA at Month 6 (Visit 4) and Month 12 (Visit 5)
- Photopic monocular logMAR UCDVA, [REDACTED], UCIVA (66 cm), and UCNVA in first operative eyes at Month 6 (Visit 4) and Month 12 (Visit 5)
- Photopic binocular logMAR uncorrected distance visual acuity (UCDVA), uncorrected intermediate visual acuity ([REDACTED], UCIVA (66 cm), and uncorrected near visual acuity (UCNVA) at Month 6 (Visit 4) and Month 12 (Visit 5)
- Photopic monocular logMAR best corrected intermediate visual acuity ([REDACTED]) and best corrected near visual acuity (BCNVA) in first operative eyes at Month 6 (Visit 4) and Month 12 (Visit 5)
- Photopic binocular logMAR [REDACTED] and BCNVA at Month 6 (Visit 4) and Month 12 (Visit 5)
- Monocular and binocular defocus curves at Month 6 (Visit 4)
- Spectacle Independence using the PRSIQ at Month 6 (Visit 4)

### 3.4 [REDACTED]

- [REDACTED]  
[REDACTED]

### 3.5 Statistical Hypotheses

#### 3.5.1 PRIMARY EFFECTIVENESS HYPOTHESES

##### 3.5.1.1 BEST CORRECTED DISTANCE VISUAL ACUITY

The null ( $H_{01e}$ ) and alternative ( $H_{11e}$ ) hypotheses for the first co-primary effectiveness variable, photopic monocular logMAR BCDVA in first operative eyes at Month 6 (Visit 4), are as follows:

$$H_{01e}: \mu_{t1e} - \mu_{c1e} \geq 0.10$$

$$H_{11e}: \mu_{t1e} - \mu_{c1e} < 0.10$$

where  $\mu_{t1e}$  and  $\mu_{c1e}$  denote the population mean photopic monocular logMAR BCDVA at 4 m in the first operative eyes at Month 6 (Visit 4) for the test and control IOLs, respectively.

##### 3.5.1.2 DISTANCE CORRECTED NEAR VISUAL ACUITY

The null ( $H_{02e}$ ) and alternative ( $H_{12e}$ ) hypotheses for the second co-primary effectiveness variable, photopic monocular logMAR DCNVA in first operative eyes at Month 6 (Visit 4), are as follows:

$$H_{02e}: \mu_{t2e} - \mu_{c2e} \geq 0$$

$$H_{12e}: \mu_{t2e} - \mu_{c2e} < 0$$

where  $\mu_{t2e}$  and  $\mu_{c2e}$  denote the population mean photopic monocular logMAR DCNVA at 40 cm in the first operative eyes at Month 6 (Visit 4) for the test and control IOLs, respectively.

#### 3.5.2 PRIMARY SAFETY HYPOTHESES

##### 3.5.2.1 SECONDARY SURGICAL INTERVENTIONS

The null ( $H_{01s}$ ) and alternative ( $H_{11s}$ ) hypotheses for the first co-primary safety variable, cumulative rate of SSIs related to the optical properties of the FINEVISION HP trifocal IOL through Month 12 (Visit 5), are as follows:

$$H_{01s}: p_{t1s} - p_{c1s} \geq 0.014$$

$$H_{11s}: p_{t1s} - p_{c1s} < 0.014$$

where  $p_{t1s}$  and  $p_{c1s}$  denote the population proportion of first operative eyes at Month 12 (Visit 5) requiring SSI related to the optical properties of the IOL for the test and control IOLs, respectively.

#### 3.5.3 SECONDARY EFFECTIVENESS HYPOTHESES

##### 3.5.3.1 DISTANCE CORRECTED INTERMEDIATE VISUAL ACUITY

The null ( $H_{03e}$ ) and alternative ( $H_{13e}$ ) hypotheses for the secondary effectiveness variable, photopic monocular logMAR DCIVA in first operative eyes at Month 6 (Visit 4), are as follows:

$$H_{03e}: \mu_{t3e} - \mu_{c3e} \geq 0$$

$$H_{13e}: \mu_{t3e} - \mu_{c3e} < 0$$

where  $\mu_{t3e}$  and  $\mu_{c3e}$  denote the population mean photopic monocular logMAR DCIVA at 66 cm in the first operative eyes at Month 6 (Visit 4) for the test and control IOLs, respectively.

### 3.6 Estimands

[Section 8.2](#) details the handling of missing data, including intercurrent events.

## 4. Study Design and Procedures

### 4.1 General Study Design

This study is a prospective, multicenter, randomized, active controlled, double masked pivotal study conducted at up to 24 study sites located in the United States. The study compares an investigational trifocal IOL, FINEVISION HP Trifocal IOL, and a commercially available monofocal IOL, AcrySof® SN60AT Monofocal IOL Model SN60AT (Alcon) [REDACTED] [REDACTED]. [REDACTED]

[REDACTED] The study will randomize approximately 501 adult subjects with operable cataracts in both eyes, which are eligible for phacoemulsification cataract surgery followed by IOL implantation. Potential subjects, after signature of the study informed consent document, will be screened for eligibility. Subjects who meet all protocol-specified eligibility criteria will be randomized at a 2:1 ratio to receive either the FINEVISION HP Trifocal IOL (test) or the AcrySof® SN60AT [REDACTED] Monofocal IOL (control) in both eyes. The first eye undergoing cataract surgery/IOL implantation will be the eye with the worse preoperative BCDVA. If BCDVA of both eyes is the same, the first operative eye will be the right eye. Subjects will undergo cataract surgery/IOL implantation in the second eye 7 to 30 days subsequent to the first eye surgery. Subjects will attend 5 post-operative evaluation visits for each eye where they will undergo ophthalmic examinations over a period of approximately 12 months (Table 1).

Standard clinical trial methods will be used to minimize bias, such as the use of a masked vision assessor as well as masking of subjects, standardized test procedures, common investigator training and common inclusion and exclusion criteria. [REDACTED]

[REDACTED]

[REDACTED]

Study visits will be referred to in all tables and listings as the visit followed by the expected study day range corresponding to the visit in parentheses to enable reviewers to understand the assessment timing without referring to the protocol visit schedule. Study visits pertaining to study endpoints in the SAP are presented as the study day, week, or month following by the visit number in parentheses to be consistent with the endpoint descriptions from the protocol. The two study visit naming conventions are linked by the visit

number; for example, “Month 6 (Visit 4)” and “Visit 4 (Day 150 to 180)” refer to the the scheduled study visits, eyes evaluated, and the acceptable visit window for each study visit:

**Table 1. Schedule of Study Visits**

Scheduled Visit	Eyes Evaluated	Visit Window
Pre-Operative Visit 0	Both Eyes	Day -90 to -1
Operative Visit 00A	1 st Operative Eye	Day 0
Post-Operative Visit 1A	1 st Operative Eye	Day 1 to 2 post Operative Visit 00A
Post-Operative Visit 2A	1 st Operative Eye	Day 7 to 14 post Operative Visit 00A
Post-Operative Visit 3A	1 st Operative Eye	Day 30 to 60 post Operative Visit 00A
Operative Visit 00B	2 nd Operative Eye	Day 7 to 30 post Operative Visit 00A
Post-Operative Visit 1B	2 nd Operative Eye	Day 1 to 2 post Operative Visit 00B
Post-Operative Visit 2B	2 nd Operative Eye	Day 7 to 14 post Operative Visit 00B
Post-Operative Visit 3B	2 nd Operative Eye	Day 30 to 60 post Operative Visit 00B
Post-Operative Visit 4	Both Eyes	Day 150 to 180 post Operative Visit 00A
Post-Operative Visit 5	Both Eyes	Day 360 to 420 post Operative Visit 00A

#### **4.2 Schedule of Visits and Assessments**

The schedule of visits and assessments is provided in the [Appendix](#).

#### **4.3 Study Treatments**

#### **4.4 Method of Assigning Subjects to Treatment Groups**

During the Pre-Operative Visit, subjects who sign the informed consent form will be assigned a unique 4-digit screening number, where the first two digits correspond to the site number. Subjects who meet eligibility criteria for cataract surgery/IOL implantation will be randomized in a 2:1 ratio to receive either the FINEVISION HP (Test) IOL or the AcrySof® SN60AT [REDACTED] Control) IOL in both eyes according to the randomization schedule. Randomization will be stratified by site. The randomization schedule will be created using computer-generated randomization methodology ([REDACTED] [REDACTED]) by an independent statistician who is not involved in the day-to-day conduct of the study. Randomization is to occur following the completion of informed consent and screening procedures.

The 4-digit subject ID will be used to identify subjects in all datasets and listings for this study.

#### **4.5 Masking and Unmasking**

In order to minimize bias, site personnel performing postoperative study assessments of visual performance, including manifest refraction, visual acuity, defocus curve testing, and contrast sensitivity will be masked to subject treatment assignment until after the final database lock (“masked assessors”). Any

unmasking of the masked assessor or any study subjects must be reported to t [REDACTED] should be made to have the same masked assessor perform the same postoperative measurements for an individual subject throughout the subject's study participation.

Subjects will also be masked to their assigned treatment group (test or control group). Any material that may indicate the subjects' assigned treatment (e.g., packaging, documents) should be removed from areas where subjects and/or masked personnel may see it. Unmasked personnel should further be instructed to avoid conversation and communication with masked personnel, subjects, and persons other than the study investigator regarding subjects' assignments, outcomes, clinical courses, and all other information potentially relevant to the study and its conduct.

## 5. Sample Size and Power Considerations

As specified in ANSI Z80.12:2007 (R2017) –C.4, a minimum of 300 subjects implanted with the investigational IOL and 150 subjects implanted with the comparator IOL must be available for analysis at Visit 5 (postoperative days 330-420).

To consider the potential loss of subjects between the time of enrollment and study completion, a total of approximately 501 subjects will be randomized and undergo surgery in this study. It is assumed that of approximately 501 subjects who undergo surgery, 51 subjects (10%) will be discontinued prematurely or lost to follow-up. Subjects will be randomized to receive either the investigational or comparator IOL in a 2:1 ratio. Of 501 subjects who undergo surgery, approximately 334 subjects will receive the investigational IOL, and 167 subjects will receive the comparator IOL. Expecting a screen failure rate of 7%, up to 539 subjects will be enrolled in the study to have 501 subjects randomized and scheduled for surgery.

### 5.1 Primary Effectiveness Variable Sample Sizes

#### 5.1.1 BEST CORRECTED DISTANCE VISUAL ACUITY

For effectiveness, 300 subjects (first operative eyes) randomized to FINEVISION HP IOL and 150 subjects (first operative eyes) randomized to AcrySof® SN60AT [REDACTED] IOL completing through Month 6 (Visit 4) yields greater than 99% power to reject  $H_{01e}$  in favor of  $H_{11e}$  and conclude the FINEVISION HP IOL is non-inferior to the AcrySof® SN60AT [REDACTED] IOL in BCDVA (logMAR) at Month 6 (Visit 4), using a one-sided t-test with an alpha level of 0.05 and assuming no difference in mean BCDVA between the IOLs, a common standard deviation (SD) of 0.10 logMAR, and a non-inferiority margin of 0.10 logMAR.

#### 5.1.2 DISTANCE CORRECTED NEAR VISUAL ACUITY

300 subjects (first operative eyes) randomized to FINEVISION HP IOL and 150 subjects (first operative eyes) randomized to AcrySof® SN60AT [REDACTED] IOL completing through Month 6 (Visit 4) will have more than 99% power to demonstrate superiority of FINEVISION HP IOL to AcrySof® SN60AT [REDACTED] IOL in DCNVA (reject  $H_{02e}$  in favor of  $H_{12e}$ ) using a two-sided t-test with an alpha level of 0.05 and assuming a true

difference in means of -0.10 logMAR (FINEVISION HP minus AcrySof® SN60A [REDACTED] SD of 0.14 logMAR.

## 5.2 Primary Safety Variable Sample Sizes

### 5.2.1 SECONDARY SURGICAL INTERVENTIONS

For safety (based on ANSI Z80.12) 300 first operative eyes with FINEVISION HP IOL and 150 first operative eyes with AcrySof® SN60AT [REDACTED] IOL completing through Month 12 (Visit 5) yields approximately 80% power to reject  $H_{01s}$  in favor of  $H_{11s}$  and conclude the FINEVISION HP IOL is non-inferior to the AcrySof® SN60AT [REDACTED] IOL in SSIs related to the optical properties of the IOL, using a one-sided Farrington-Manning score test with an alpha level of 0.05 and assuming the true proportions of SSIs related to the optical properties of the FINEVISION HP IOL and of the AcrySof® SN60AT [REDACTED] IOL are both equal to 0.001, and a non-inferiority margin of 0.014 (1.4%). Similarly, ISO 11979-7 specifies that a minimum of 300 subjects should complete a clinical evaluation of an IOL to obtain appropriate specificity around AE and visual acuity rates.

## 5.3 Secondary Effectiveness Variable Sample Sizes

### 5.3.1 DISTANCE CORRECTED INTERMEDIATE VISUAL ACUITY

300 subjects (first operative eyes) randomized to FINEVISION HP IOL and 150 subjects (first operative eyes) randomized to AcrySof® SN60AT [REDACTED] IOL completing through Month 6 (Visit 4) will have more than 99% power to demonstrate superiority of FINEVISION HP IOL to AcrySof® SN60AT [REDACTED] IOL in DCIVA (reject  $H_{03e}$  in favor of  $H_{13e}$ ) using a two-sided t-test with an alpha level of 0.05 and assuming a true difference in means of -0.10 logMAR (FINEVISION HP minus AcrySof® SN60AT [REDACTED]) with a common SD of 0.14 logMAR.

[figure not shown]
## 5.4 [REDACTED]s

### 5.4.1 [REDACTED] [REDACTED]

## 6. Data Preparation

### 6.1 Input Data

Study data will primarily be recorded on the eCRFs supplied by [REDACTED] In addition, the following study data which is not captured directly within the EDC system but is obtained from external vendors will also be included for analysis. These data sources are described in detail in data transfer agreements developed between data management and the respective external laboratory or reading center:

- IOL axis orientation

When all prerequisites for database lock have been met, including availability of all masked external data, the database will be locked. Following database lock, approval will be obtained from the Sponsor to unmask the study. Any changes to the database after data have been locked can only be made with the approval of the Sponsor in consultation with [REDACTED]

Final analysis will be carried out after the following have occurred:

- Database lock has occurred, including receipt of all final versions of external vendor data, with written authorization provided by appropriate [REDACTED] and Sponsor personnel.
- Protocol deviations have been identified and status defined (major/minor deviations).
- Analysis populations have been determined.
- Randomized treatment codes have been unmasked.

## 6.2 Output Data

Data from the EDC system and external data will be transferred to [REDACTED] Biostatistics and mapped to analysis datasets using the Analysis Data Model (ADaM). Both raw and ADaM-formatted data will be used to create the subject listings, while all tables and figures will be based on the ADaM-formatted data.

# 7. Analysis Populations

## 7.1 Intent-to-Treat Population

The Intent-to-Treat (ITT) Set will include all randomized subjects (eyes). Summaries and analyses based on the ITT Set will analyze subjects as randomized.

## 7.2 All-Implanted Analysis Set

The All-Implanted Analysis Set (AAS) will include all subjects (eyes) with successful IOL implantation with at least one postoperative visit. Summaries and analyses based on the All-Implanted Analysis Set will analyze subjects as treated.

## 7.3 Best Case Set

The Best Case Set will include subjects with all of the following characteristics:

- No major protocol deviations potentially affecting any of the primary effectiveness endpoints (BCDVA, DCNVA). Major protocol deviations that may potentially affect the primary effectiveness endpoints include, but are not limited to:
  - Inclusion of ineligible subjects
  - Implantation of incorrect IOL
  - Missed assessments for effectiveness endpoints at Month 6 (Visit 4)
  - Receipt of medication likely to interfere with visual performance at Month 6 (Visit 4)

- At least one eye implanted with a study lens
- No clinically significant preoperative ocular pathology in the first operative eye, including any of the following present prior to the Operative Visit:
  - Pseudoexfoliation of lens capsule
  - Glaucoma
  - Uveitis
  - Retinal detachment
  - Diabetic retinopathy
  - Macular degeneration
  - Amblyopia
  - Other preoperative pathologies that are likely to affect central acuity
- No macular degeneration detected at any time in the first operative eye
- No previous surgery for the correction of refractive errors in the first operative eye

Summaries and analyses based on the Best Case Set will analyze subjects as treated.

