## 5.2 EXCLUSION CRITERIA

Subjects with any of the following diseases, surgeries or conditions are ineligible for study participation. Subjects may not participate if either eye meets any of the ocular exclusion criteria:

- 1) History or presence of, or predisposition to, degenerative visual disorders (e.g., macular degeneration, retinal detachment, proliferative diabetic retinopathy, or other retinal disorders) predicted to result in BCDVA worse than 0.2 LogMAR (20/32 Snellen) in either eye during the study participation period.
- 2) Significant anterior segment pathology in either eye that might increase intraoperative risk or compromise IOL stability (e.g., pseudoexfoliation syndrome)
- 3) Reasonably expected to require secondary ocular surgical intervention or laser treatment other than YAG capsulotomy in either eye during the study participation period.
- 4) Presence of one or more clinically significant corneal abnormalities in either eye, including corneal dystrophy, irregularity, or edema per the Investigator's medical opinion.
- 5) Previous intraocular, corneal, or retinal detachment surgery, including corneal transplant, LASIK, astigmatic keratotomy and limbal relaxing incisions in either eye
- 6) Rubella, congenital, traumatic or complicated cataract in either eye
- 7) Preoperative keratometric astigmatism  $> 1.0$  D or irregular corneal astigmatism in either eye (Note: corneal incisions intended to reduce astigmatism are not permitted)
- 8) Clinically significant ocular inflammation or infection present  $\leq 30$  days in either eye prior to the Preoperative Visit.
- 9) Presence or history of one or more severe/serious ocular conditions (e.g., glaucoma, uveitis, ocular infection, severe dry eye) in either eye, or any other unstable medical condition (e.g., uncontrolled diabetes) that in the opinion of the Investigator would put the subject's health at risk, confound the results of the study and/or prevent the subject from completing all study visits.
- 10) Use of medications known to interfere with visual performance, pupil dilation, or iris structure  $\leq 30$  days prior to the Preoperative Visit.
- 11) Participation in any study of an investigational, interventional product within 30 days prior to the Preoperative Visit or at any time during the study period.
- 12) Pregnant or nursing females.

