## 14.2 Defocus Curves

Defocus curve testing will be performed under photopic conditions at a test distance of 4 m at Month 6 (Visit 4) and Month 12 (Visit 5). [REDACTED]

[REDACTED] Each subject will be defocused with spherical lenses from +2.00 D through -4.00 D over the subject's manifest distance correction in -0.50 D increments.

Monocular and binocular defocus curves from Month 6 (Visit 4) and Month 12 (Visit 5) based on the Best Case Set will be summarized by treatment group and visit utilizing continuous descriptive statistics. Defocus curve summaries by treatment group will also be presented for each of the following post-operative photopic pupil size groups:

- Small (< 2.5mm)
- Medium (2.5mm to  $\leq$  4mm)
- Large (> 4mm)

For summaries of binocular defocus curves by pupil size, the average pupil size computed over both eyes will be used to determine the pupil size subgroup.

The defocus curve means will be plotted for each treatment group and for each pupil size group with error bars representing one standard deviation.

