### **15.1 Primary Safety Analyses**

The co-primary safety endpoints are:

- Cumulative rate of SSIs related to the optical properties of the IOL in first operative eyes through Month 12 (Visit 5)
- Mean monocular distance contrast sensitivity (mesopic with and without glare at 1.5, 3, 6, and 12 cpd measured at 2.5m, and photopic with and without glare at 3, 6, 12, and 18 cpd, measured at 2.5 m) in first operative eyes at Month 12 (Visit 5)

The analyses of co-primary safety variables will be based on first operative eyes and repeated as supportive analyses using second operative eyes as well as all operative eyes.

Secondary surgical interventions related to the optical properties of the IOL will be evaluated using discrete summary statistics. Noninferiority of FINEVISION HP IOL compared to AcrySof® SN60AT [REDACTED] IOL in the proportions of first operative eyes with secondary surgical interventions related to the optical properties of the IOL will be evaluated using two-sided 90% Farrington method CIs around the difference in proportions between the FINEVISION HP IOL and AcrySof® SN60AT [REDACTED] IOL. If the upper limit of the CI is less than 0.014 (1.4%), then  $H_{01s}$  will be rejected in favor of  $H_{11s}$ , and the FINEVISION HP IOL will be considered statistically non-inferior to the AcrySof® SN60AT [REDACTED] IOL in rate of SSIs related to optical properties of the IOL.

SAS® code similar to the code below will be used to compute the Farrington CIs:

```
proc freq data = indata;
  table TRTAN * resp / nocol nopercent riskdiff(noninf margin = 0.014
method = fm column = 1) alpha = 0.05;
  ods output CrossTabFreqs = freqs(where = (resp = "Y")) PdiffNoninf =
cis;
run;

data freqs;
  set freqs;
  freq = Frequency;
  pct = RowPercent;
run;

/* Adjust CIs to convert limits to percentages and convert diff estimate, CI
for p_control - p_test to diff estimate, CI for p_test - p_control */
data cis;
  set cis;
  diff_pct = -100*Estimate;
  diff_ci_LCL = -100*UpperCL;
  diff_ci_UCL = -100*LowerCL;
run;
```

where

- TRTAN equals 1 for the test IOL (FINEVISION HP IOL) and 2 for the control IOL (AcrySof® SN60AT [REDACTED] IOL)
- resp equals "Y" if a subject has any SSIs related to the optical properties of the IOL or "N" if a subject has no SSIs related to the optical properties of the IOL.

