Monocular best-corrected distance contrast sensitivity (mesopic with and without glare at 1.5, 3, 6, and 12 cpd measured at 2.5 m, and photopic with and without glare at 3, 6, 12, and 18 cpd, measured at 2.5 m) in first operative eyes based on the Best Case Set will be summarized by treatment group using continuous summary statistics. The treatment group difference (mean Test group contrast sensitivity minus mean Control group contrast sensitivity) in log units will be presented by testing condition and frequency. Additionally, for each testing condition and frequency, the 5th percentile for the control group log contrast sensitivity will be determined, and the number and percentage of subjects in the investigational arm who have achieved a log contrast sensitivity lower than this value will be reported.

As a subgroup analysis, the primary analysis of the cumulative rate of SSIs related to the IOL will be repeated for the following Pre-Operative Visit photopic pupil size subgroups: small (< 2.5 mm), medium (2.5 to ≤ 4mm), and large (> 4 mm). Similar subgroup analyses will be performed for mean monocular best-corrected distance contrast sensitivity at Month 12 (Visit 5) with subgroups based on photopic pupil size at Month 12 (Visit 5) for photopic lighting conditions or mesopic pupil size at Month 12 (Visit 5) for mesopic lighting conditions.

As poolability analyses, the co-primary safety endpoints will be summarized by treatment group and site using discrete or continuous summary statistics as appropriate.

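### The Best Case Set screens only the first operative eye for pathology and macular degeneration, yet it also serves binocular defocus curves and, by natural reading, second-eye and all-eye contrast sensitivity

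*SAP*

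**What the plan says.** SAP 7.3 defines the set by subject: "The Best Case Set will include subjects with all of the following characteristics". Three of its criteria concern the condition of the eye, and each names one eye only:

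- "No clinically significant preoperative ocular pathology in the first operative eye", followed by a list that includes glaucoma, diabetic retinopathy, macular degeneration and amblyopia;
- "No macular degeneration detected at any time in the first operative eye", which also covers onset after surgery;
- a bar on earlier refractive surgery, again judged in that eye alone.

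Protocol 9.3 has the same definition. Neither document gives a second-eye or both-eyes version.

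The set is used in three places that matter here.

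- **Contrast sensitivity, first eyes (SAP 15.1).** The summary is "in first operative eyes based on the Best Case Set will be summarized by treatment group using continuous summary statistics". It includes the share of test subjects who score below the control group's 5th percentile, for each lighting condition and spatial frequency.
- **Contrast sensitivity, other eyes (SAP 15.1 and Protocol 9.4.6).** The co-primary safety analyses are "repeated as supportive analyses using second operative eyes as well as all operative eyes". No analysis set is named for the repeats.
- **Defocus (SAP 14.2 and Protocol 9.4.11).** The SAP summarises "Monocular and binocular defocus curves from Month 6 (Visit 4) and Month 12 (Visit 5) based on the Best Case Set".

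**The concern.** A Best Case Set is meant to show how the lens performs in eyes free of disease that would itself limit vision. Here one eye's condition decides membership for both. A subject with a clean first eye and a diseased second eye meets every eye-condition criterion, so the diseased eye enters the second-eye, all-eye and binocular summaries. A subject who fails on the first eye is removed altogether, healthy second eye included.

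The contrast sensitivity summary is the more sensitive of the affected outputs, because its reference point is the lower tail of the control distribution. If diseased control eyes sit in that tail, a few of them pull the 5th percentile down, and fewer test eyes fall below it. A real loss of contrast with the test lens would then look smaller in second eyes than it is.

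**Working it through.** **Step 1. Set the definition beside its uses.**

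| Output on the Best Case Set | Eye(s) analysed | Eye screened in 7.3 | Match? |
|---|---|---|---|
| Sensitivity Analysis III, BCDVA and DCNVA (SAP 13.1.3), and its repeat for DCIVA (13.2) | First | First | Yes |
| Contrast sensitivity, main summary (15.1) | First | First | Yes |
| Contrast sensitivity, supportive repeats (15.1; set inferred) | Second; all | First | No |
| Binocular defocus (14.2; set explicit) | Both | First | No |

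**Step 2. See what eligibility already removes from second eyes.** Protocol 5.1 and 5.2 apply ocular criteria to both eyes.

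- Exclusion 5 bars earlier intraocular and corneal surgery in either eye and names LASIK. The prior-refractive-surgery criterion is therefore essentially covered.
- Exclusion 2 covers significant anterior segment pathology and names pseudoexfoliation.
- Exclusion 9 covers severe or serious conditions and names glaucoma and uveitis, subject to investigator opinion.
- Inclusion 4 requires projected BCDVA of 0.2 logMAR or better in each eye.
- Enrolment of an ineligible subject is listed in 7.3 as a major deviation. It counts there only if it may affect BCDVA or DCNVA, and as primary endpoints both are measured in first eyes.

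**Step 3. See what is left.**

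- Exclusion 1 bars retinal disease only when it is "predicted to result in BCDVA worse than 0.2 LogMAR (20/32 Snellen) in either eye during the study participation period". Milder macular degeneration or diabetic retinopathy can be enrolled.
- Amblyopia is not a named exclusion, so an amblyopic eye projected to reach 0.2 logMAR can be enrolled.
- Macular degeneration first detected after surgery is not an eligibility failure. The any-time criterion in 7.3 catches it, but in the first eye only.

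**Step 4. Illustrate the size for second-eye contrast sensitivity.** The plan gives no figure to reproduce. From the documents: 150 control and 300 test first eyes at Visit 5 (SAP 5.2.1), carried over here to second eyes. Assumed: *k* diseased control eyes, *m* = 2*k* diseased test eyes (equal prevalence under 2:1 randomisation), diseased eyes ranked lowest, normal log contrast, and a true loss of 0.5 SD with the test lens.

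The control 5th percentile lies at rank 0.05 × 150 = 7.5. Among healthy control eyes this is the fraction

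p = (7.5 − k) / (150 − k), with z = Φ⁻¹(p).

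Healthy test eyes below the threshold: h = Φ(z + 0.5). Share of all test eyes flagged: [m + (300 − m) × h] / 300.

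| k | m | p | z | h | Share flagged |
|---|---|---|---|---|---|
| 0 | 0 | 5.0% | −1.645 | 12.6% | 12.6% |
| 2 | 4 | 3.7% | −1.785 | 9.9% | (4 + 296 × 0.0995)/300 = 11.1% |
| 4 | 8 | 2.4% | −1.978 | 7.0% | (8 + 292 × 0.0697)/300 = 9.5% |

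The drop is about 1.5 points with two diseased control eyes and 3.2 points with four. With no true loss, h = p and the share stays at 5% (for k = 2, (4 + 296 × 0.0372)/300 = 5.0%). The mechanism therefore weakens a real difference and does not create a false one.

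No calculation is offered for binocular defocus, because the documents give nothing from which to size it.

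**The case against.** Four arguments can be made against the point.

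**The set fits its purpose.** It is built around BCDVA and DCNVA in first eyes and is coherent for Sensitivity Analysis III and for first-eye contrast sensitivity. This stands. The mismatch arises only where the set is carried to other eyes.

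**The set for second-eye contrast sensitivity is inferred.** SAP 15.1 attaches the Best Case Set to first operative eyes, and SAP 15 defaults to the Safety Set. This stands as a limit on certainty. A repeat of an analysis would naturally keep its analysis set. If the default applied instead, second eyes would have no pathology exclusion at all, and first-eye and second-eye results would describe differently selected eyes. Both readings need a sentence in 15.1, and binocular defocus is affected under either.

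**Eligibility does most of the work.** This largely stands, as Step 2 shows. In addition, the first eye is the one with the worse preoperative BCDVA, or the right eye if the two are equal, so second eyes start with equal or better acuity. What remains is narrower but real. Diseased second eyes can stay in; the documents do not show that any will.

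**Nothing decisive depends on it.** This stands. A reader might infer that a second-eye safety criterion could be passed wrongly. The documents contain no such criterion. SSI is the only safety endpoint with a hypothesis, and the 5th-percentile share is simply reported, with no limit or test. A reader might also count diseased eyes in the control arm alone and take the falls to be to about 9.9% and 7.0%. Those are the shares among healthy test eyes only. Randomisation gives no reason to expect disease in one arm alone, and diseased test eyes would be flagged as well.

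**Conclusion.** The point holds in limited form. The pathology and any-time macular degeneration criteria select subjects on the first eye, while the set is used explicitly for binocular defocus and, on the natural reading, for second-eye and all-eye contrast sensitivity. This is a stated rule that can select the wrong eyes, and it is more than a missing detail. The affected outputs are supportive or descriptive. First-eye results, the BCDVA and DCNVA success criteria and the SSI comparison do not change.

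Under the assumptions in Step 4, the share of test second eyes flagged falls from 12.6% to about 11.1% or 9.5%. That range rests on the assumed 0.5 SD loss, the assumed counts (2 or 4 of 150, that is 1.3% or 2.7%) and worst-rank placement. Eyes with disease mild enough for 0.2 logMAR need not rank lowest, so the effect could be smaller. The documents do not give the number of such eyes. Loss of healthy second eyes costs supportive data; no bias from it has been shown.

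**What to change.** In SAP 7.3, apply the preoperative pathology and any-time macular degeneration criteria to the eye being analysed: the first eye for first-eye tables, the second eye for second-eye tables, each eye on its own for all-eye tables, and both eyes for binocular defocus. The prior-surgery criterion can follow the same pattern for consistency, although exclusion 5 already covers it. In SAP 15.1, state that second-eye and all-eye contrast sensitivity use this eye-level Best Case Set. Record the departure from Protocol 9.3 in SAP 19.

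The cost is a few lines of SAP text and one eye-level flag, derived from the medical history, slit-lamp and fundus data already scheduled. SAP 6.1 requires analysis populations to be determined before the final analysis, and the flag should be fixed at that step, before treatment codes are unmasked. First-eye tables need no reprogramming.
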